Participants will be identified and recruited from inpatient units at Jackson Memorial Hospital using the electronic health record. At consent, participants will be asked to sign a HIPAA waiver to allow access to their medical record for 60 days after discharge. 60 participants will be randomly assigned to one of two intervention conditions: 1) Meds to Beds, patients receive medication in-hand at discharge from the hospital, and 2) standard care (patient pickup at the pharmacy) comparison group. Adherence to medication will be measured with 1) self-report Adherence to Refills and Medications Scale (ARMS), and 2) pharmacy refill data. Health will be assessed with the self-report PROMIS 10, a measure developed by researchers for patient-reported evaluation of global health. Information on hospital readmission, other hospital visits, and deaths will be obtained from the electronic health record. Feasibility will be determined by tracking the number of patients who receive medications before discharge in the Meds to Beds intervention and by asking patients at follow-up how they received their discharge medications and about their experiences with healthcare. Acceptability will be assessed with 2 questions created for this study. A self-report questionnaire with 7 items created for this study will assess theoretical mechanisms of change for the Meds to Beds intervention. Self-report measures will be administered in-person before randomization, and/or about 30 days post-discharge by telephone or in-person. Prescription refill and other information from the electronic health record will be monitored for up to 60 days post-baseline in order to collect data about the period 30 days post-discharge. Measures are either available in English and Spanish from the authors, or will be translated using a translation back-translation approach.

6) Data and Specimen Banking*

There will be no specimen banking.

7) Data Management*

Protection of patient privacy and confidentiality will be maintained in highest priority at all times. All files will be kept in a locked office and data stored on a secured drive. All personally identifying patient information will be kept separate from patient data at all times.

8) Risks to Subjects*

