This study is expected to be of minimal risk to participants. Special care will be taken to ensure patients do not confuse participation in this study with their treatment plan, and continue to contact their regular providers for any issues or questions regarding their medication or health.

9) Potential Benefits to Subjects*

This study provides no direct benefit to participants.

10) Vulnerable Populations*

This study will not include pregnant women, prisoners, children or cognitively impaired adults.

11) Setting

Some study data will be collected at inpatient units at Jackson Memorial Hospital, with follow-up via telephone or in-person with these participants.

12) Resources Available

[name], BSN, RN, PhD is a fourth-year doctoral student in Nursing at the University of Miami School of Nursing and Health Studies. She has spent the past three years researching cardiovascular disease and medication adherence, including a participating in graduate-level nursing clinical at Jackson Memorial Hospital. She is fully bilingual in English and Spanish, and will be responsible for all data collection.

13) Prior Approvals

Approval of Jackson Memorial Hospital will be obtained before commencing this study.

14) Recruitment Methods

A partial HIPAA waiver will be requested to identify patients admitted to Jackson Memorial Hospital with a heart failure diagnosis who may qualify for the investigation. These patients will be approached at bedside by a known person such as a nurse or physician and invited to participate in the study. If interested in participating patients will be screened by researcher with a preliminary questionnaire regarding medical history and contact information. Qualifying patients will be asked to sign a consent form. At the time of inclusion in the study, participants will receive a gift card worth \$20 as compensation. In addition, participants will receive \$50 as compensation for completing the telephone follow-up portion of the study.

15) Local Number of Subjects

There will be up to 60 participants (30 Meds to Beds, 30 standard care).

16) Confidentiality

Patient confidentiality will be maintained at all times; they will only be contacted by one researcher. Data and responses will be linked using a numerical ID; a linking list with names matched to ID will be stored separately from data by the principal investigator in secure location.

IRB Study Number: HRP-503 20160741

Version #6 July 19, 2018

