Hypothesis 3. Participants in the intervention group will have lower deterioration in physical health from baseline to 30 days after discharge than the control group.

This hypothesis will be tested using repeated measures ANOVA.

Hypothesis 4. Participants in the intervention group will have a lower proportion of readmissions and deaths than the control group.

Hypothesis 4A. The intervention group will have a lower proportion of readmissions at 30 days than the control group.

Hypothesis 4B. The intervention group will have a lower proportion of deaths at 30 days than the control group.

These hypotheses will be tested using a chi-square test.

Hypothesis 5. Participants in the intervention group will have lower increases in mechanisms of action variables 30 days after discharge than the control group.

Hypothesis 5A. The average length of time (in 0-30 days) before beginning a prescription medication regimen for participants in the intervention group will be lower than among those in the control group.

Hypothesis 5B. Participants in the intervention group will report lower increases in Personal Inconvenience (*Patient Factor* of belief that medications will be difficult to obtain) than those in the control group.

Hypothesis 5C. Participants in the intervention group will report a higher score in in Immediacy of Benefit (*Therapy-related factor*) than those in the control group.

Hypothesis 5D. Participants in the intervention group will report lower increases in Fatigue (*Condition-related Factor*) than those in the control group.

Hypothesis 5E. Participants in the intervention group will report lower increases in Family Inconvenience (*Social/economic factor* of reduced family support) than those in the control group.

Hypothesis 5F. Participants in the intervention group will report lower increases in Prescription-related Paperwork (*Health care team / health system factor*) than those in the control group.

Hypotheses 5A-5F will be tested using ANOVA or repeated measures ANOVA, depending on the number of times the outcome is assessed.

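### Hypothesis 3: analysing 30-day physical health by ANCOVA on baseline would usually give a tighter estimate than repeated measures ANOVA, at almost no cost

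*SAP*

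**What the plan says.** SAP, Hypothesis 3, predicts that the intervention arm will show "lower deterioration in physical health from baseline to 30 days after discharge than the control group". The whole analysis statement is "This hypothesis will be tested using repeated measures ANOVA". It does not say whether group-by-time or the group main effect carries the test, and it names no covariate. ANCOVA appears nowhere in the SAP.

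Protocol section 5 gives the instrument ("Health will be assessed with the self-report PROMIS 10") and the timing: "Self-report measures will be administered in-person before randomization, and/or about 30 days post-discharge by telephone or in-person". A self-report outcome therefore has at most two occasions, and Hypothesis 3 needs both. Assignment is random ("60 participants will be randomly assigned to one of two intervention conditions"), and Protocol section 15 sets the size: "There will be up to 60 participants (30 Meds to Beds, 30 standard care").

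For the mechanism outcomes the SAP states: "Hypotheses 5A-5F will be tested using ANOVA or repeated measures ANOVA, depending on the number of times the outcome is assessed". Items 5B, 5D, 5E and 5F are worded as increases, which implies a baseline. Items 5A and 5C are not.

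**The concern.** With two arms and two occasions, the group-by-time test in a repeated measures ANOVA is a comparison of mean change scores. A change score subtracts the whole baseline value, however weakly baseline predicts follow-up. When the correlation is modest, that adds noise. ANCOVA estimates how much of the baseline to subtract. Because baseline is taken before randomization, the arms have equal expected baselines and both methods target the same treatment effect.

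At stake is precision, not validity. With at most 30 patients per arm, the confidence interval for the physical health effect will be wide, and the choice of model is one of the few ways to narrow it without more patients. Leaving the tested term unnamed adds a smaller risk: the model could end up being chosen after the results are known.

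**Working it through.** **Inputs from the documents.** Two randomized arms, up to 30 each (N = 60); two occasions for Hypothesis 3. The plan states no power or precision figure, so there is none to reproduce.

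**Assumed, because the documents are silent.** Correlation rho from 0.3 to 0.9; k = 30-day SD / baseline SD of 0.8, 1 or 1.25; two-sided 5% level; an illustrative true effect of 0.6 of the 30-day SD; 30 per arm, or 25 per arm with both scores.

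**Step 1: the identity.** On one simulated data set of 30 + 30, the group-by-time F on 1 and 58 df was 3.914 and the squared change-score t was 3.914. The group main effect on the same data gave F = 1.93, so the unnamed term matters.

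**Step 2: variances, in 30-day SD units.**
- Change score: 1 + 1/k² − 2·rho/k, which is 2(1 − rho) when k = 1.
- ANCOVA: (1 − rho²)·(N − 3)/(N − 4). The last factor is the price of estimating the slope; at N = 60 it is 57/56 = 1.018.
- Without that factor, change-score variance minus ANCOVA variance is (1/k − rho)², which is never negative. So ANCOVA's expected loss at N = 60 is at most about 1.8% of variance, whatever rho and k.

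Example at k = 1, rho = 0.5: change 2(0.5) = 1.000; ANCOVA 0.75 × 1.018 = 0.763; reduction 24%. The standard error shrinks by a factor √0.763 = 0.874, so the interval is about 13% shorter.

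**Step 3: net variance reduction at N = 60.**

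| rho | k = 0.8 | k = 1 | k = 1.25 |
|---|---|---|---|
| 0.3 | 49% | 34% | 20% |
| 0.5 | 42% | 24% | 9% |
| 0.7 | 36% | 13.5% | 0% |
| 0.8 | 35% | 8% | −2% |

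At k = 1 and rho = 0.9 it is 3%. With equal SDs the sign reverses where (1 + rho)/2 × 57/56 = 1, that is, rho = 0.965.

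**Step 4: power for 0.6 SD** (noncentral t; 58 df for change, 57 for ANCOVA at N = 60).

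| Setting | rho | Change score | ANCOVA |
|---|---|---|---|
| k = 1, 30 per arm | 0.3 | 49% | 66% |
| | 0.5 | 63% | 74% |
| | 0.7 | 84% | 89% |
| | 0.8 | 95.1% | 96.5% |
| k = 1, 25 per arm | 0.3 | 42% | 58% |
| | 0.5 | 55% | 66% |
| | 0.7 | 77% | 82% |
| k = 1.25, 30 per arm | 0.5 | 70.3% | 74.4% |
| | 0.7 | 88.7% | 88.7% |
| | 0.8 | 96.8% | 96.5% |
| k = 0.8, 30 per arm | 0.7 | 71.7% | 88.7% |

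**Step 5: simulation check.** With 40,000 trials per setting (30 per arm, k = 1), variance fell by 34.5%, 23.6% and 13.2% at rho 0.3, 0.5 and 0.7. Power was 48.9 v 66.2%, 63.0 v 74.5% and 84.4 v 89.0%. A separate simulation with a 0.5 SD effect found both estimators unbiased.

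**Step 6: if the group main effect were meant.** Averaging in a pre-randomization score halves a 0.6 SD effect to 0.3. At k = 1 and rho = 0.5 the averaged score has variance (1 + 0.5)/2 = 0.75, so the standard error is √(0.75 × 2/30) = 0.224 and power is about 26%, against 63% and 74% above.

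**The case against.** The strongest reply is that nothing here is wrong. The planned test answers the question Hypothesis 3 asks and holds its error rate. The trial is a pilot with feasibility and acceptability among its aims. No primary outcome is designated, and no power claim depends on this model. That is correct, and it is why the point is one of efficiency.

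A second reply is that the gain cannot be known. Rho, both SDs, the effect size and the number of completers are all assumed, and the results in the tables run from a 49% reduction to a 2% loss. Baseline is taken in hospital and follow-up about a month after discharge, so equal SDs should not be presumed. This also stands: the power figures are illustrations, not forecasts. It does not decide the matter, because the expected loss is capped at about 1.8% of variance while the possible gain is many times that. The sponsor does not need to know rho to prefer ANCOVA.

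Third, the reach beyond Hypothesis 3 is uncertain. The protocol's and/or timing leaves open which items have a baseline. The mechanism questionnaire has 7 study-created items, so some constructs may rest on a single item, where a linear baseline adjustment is less secure. No baseline for the adherence questionnaire is stated. The recommendation for those outcomes is therefore conditional.

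Finally, a confidence interval could be reported from change scores too, so it is not an argument for ANCOVA.

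**Conclusion.** The point holds as an improvement that should be made, not as an error. If Hypothesis 3 is tested by group-by-time, the analysis is a change-score t-test, and ANCOVA on the same baseline will usually be more precise: by roughly a quarter of the variance at rho 0.5 with equal SDs and 60 patients, more at lower correlations or when scores are less variable at 30 days. The gain is close to nil when rho is very high or when the baseline SD is near rho times the 30-day SD. These sizes rest on assumed correlations and SD ratios; the power figures also assume a 0.6 SD effect and a two-sided 5% level. The cap on the loss at N = 60 does not depend on rho or the SD ratio. If the SAP intends the group main effect, the case for change is stronger.

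**What to change.** - In the SAP, state that Hypothesis 3 is analysed by ANCOVA of the 30-day physical health score on arm and baseline score, reporting the adjusted mean difference with its 95% CI.
- List which Hypothesis 5 items are collected both before randomization and at 30 days, and use the same model for those.
- Apply it to Hypothesis 1B only if the adherence questionnaire is also taken at baseline.

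For Hypothesis 3 this is one sentence, with no new patients, visits or instruments. The statistical cost is one residual degree of freedom (57 instead of 58), about 1.8% variance inflation at N = 60 from estimating the slope, and an assumed linear relation between the baseline and 30-day scores.

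### Hypothesis 5C is worded against the Hypothesis 5 heading, and its test is set by the number of assessments, which the documents do not state, instead of by the hypothesis (minor)

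*SAP*

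**What the plan says.** The heading of Hypothesis 5 in the SAP predicts that the intervention arm "will have lower increases in mechanisms of action variables 30 days after discharge than the control group". Four of the five questionnaire hypotheses, 5B, 5D, 5E and 5F, follow it; for example, "Participants in the intervention group will report lower increases in Fatigue". Hypothesis 5C does not: the intervention arm "will report a higher score in in Immediacy of Benefit". 5C has no time point of its own, so 30 days comes only from the heading. Hypothesis 5A concerns "The average length of time (in 0-30 days) before beginning a prescription medication regimen", which is not an increase either, although its direction (lower) agrees with the heading.

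One rule covers all six: "Hypotheses 5A-5F will be tested using ANOVA or repeated measures ANOVA, depending on the number of times the outcome is assessed". The SAP does not say which term of the repeated measures model is the test.

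On measurement, section 5 of the protocol (Procedures Involved) says: "A self-report questionnaire with 7 items created for this study will assess theoretical mechanisms of change". On timing it says: "Self-report measures will be administered in-person before randomization, and/or about 30 days post-discharge by telephone or in-person". No schedule is given item by item, and no item wording or scoring direction.

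**The concern.** Two things look wrong.

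First, the wording. Randomisation makes the arms equal at baseline in expectation. A higher 30-day score in the intervention arm therefore means, on average, a greater increase in that arm. Immediacy of Benefit is listed under Hypothesis 5 as one of the mechanism variables, so a success on 5C runs against the heading as written.

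Second, the test. 5C is a statement about a level, but its analysis follows from how many times the item happens to be asked. If the whole questionnaire is given at both visits, 5C goes to repeated measures ANOVA, where neither standard term is a good match. The between-group main effect compares average scores, but half of that average was measured before randomisation, when no effect can exist. The group-by-time term compares changes, which is not what 5C states. With no term named, the choice could be made after the data are seen.

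**Working it through.** The documents give no alpha, effect size, SD, correlation or power for this hypothesis, so there is no planned figure to reproduce.

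**Step 1: how often is 5C measured?** The increases in 5B, 5D, 5E and 5F need a pre-randomisation value, and the protocol describes a single mechanism questionnaire, so two administrations of the 5C item are plausible. The timing sentence also allows a single one, and the level wording of 5C fits that. The documents do not settle it.

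**Step 2: what follows in each case?**

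- Asked once, at 30 days: ordinary ANOVA of the 30-day score. This tests 5C as written.
- Asked twice: repeated measures ANOVA, by either the group main effect or group-by-time.

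**Step 3: what would each test deliver?**

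Input from protocol section 15: 30 per arm. Assumed: two-sided 5%, SD 1 at both visits, no true baseline difference, 30-day effect d, baseline-to-30-day correlation r of 0.3, 0.5 or 0.7, no dropout. The value d = 0.74 is chosen because a plain 30-day comparison with 30 per arm then has about 80% power.

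Expected difference and SD of the quantity compared:

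- 30-day score: d, SD 1
- Group main effect (mean of the two visits): d/2, SD √((1 + r)/2)
- Group-by-time (change): d, SD √(2(1 − r))
- 30-day score adjusted for baseline: d, SD √(1 − r²)

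The noncentrality is the difference divided by SD × √(2/30), with √(2/30) = 0.258. Power comes from the noncentral t with 58 degrees of freedom. For the adjusted comparison, r is treated as known and the one lost degree of freedom is ignored.

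Example at d = 0.74, r = 0.5:

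- 30-day score: 0.74 / 0.258 = 2.87, power 80%
- Main effect: 0.37 / (0.866 × 0.258) = 1.65, power 37%
- Group-by-time: 0.74 / (1 × 0.258) = 2.87, power 80%
- Adjusted 30-day score: 0.74 / (0.866 × 0.258) = 3.31, power 90%

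| Test of 5C, d = 0.74 | r = 0.3 | r = 0.5 | r = 0.7 |
|---|---|---|---|
| 30-day score, unadjusted | 80% | 80% | 80% |
| Group main effect | 42% | 37% | 33% |
| Group-by-time | 66% | 80% | 95% |
| 30-day score, baseline as covariate | 84% | 90% | 98% |

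At d = 0.5 the ordering is the same: 48% for the unadjusted 30-day score; 22%, 20% and 18% for the main effect; 36%, 48% and 69% for group-by-time; 51%, 59% and 76% for the adjusted score.

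**Step 4: check by simulation.** With 20,000 simulated trials at each r and a true 30-day effect of 0.74, the main-effect contrast averaged 0.37 and the group-by-time contrast 0.74. Halving therefore occurs for the main effect only.

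**The case against.** The strongest reply is that the SAP, read as a whole, already points to a sensible analysis. Its other level-worded comparisons of arms (1A, 1B, 2B and 2C) go to ANOVA, and its change hypothesis on physical health (Hypothesis 3) goes to repeated measures ANOVA. By that pattern 5C is a single 30-day score tested by ANOVA. If it is measured twice, Hypothesis 3 suggests that group-by-time is the intended term, and that term is not diluted. The heading is only a loose summary: 5A to 5F are tested separately, there is no overall test of Hypothesis 5, and no analysis result changes because heading and sub-hypothesis disagree.

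Much of this stands. A reader might infer that the plan halves the effect on Immediacy of Benefit and will probably miss it. The documents do not support that. It needs the item to be measured twice and the main effect to be the tested term, and neither is stated. A reader might also infer that a favourable 5C would formally count against Hypothesis 5; with no joint test, it would not. The wording conflict is mainly editorial.

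What the reply does not remove is the gap. The pattern elsewhere is an inference, whereas the rule written for 5C is the number of assessments. If the item is asked twice, group-by-time tests a greater increase and not the higher score that 5C states, and at r = 0.3 it has less power than simply comparing 30-day scores (66% against 80%).

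**Conclusion.** The point holds in a limited form. The direction and type of 5C conflict with the heading on the face of the text. The analysis of 5C is not determined by the documents, because neither the number of assessments nor the tested repeated measures term is given.

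If the item is asked once, the wording conflict is all that remains. If it is asked twice, power at d = 0.74 could lie anywhere from 33% to 95%, depending on the term chosen and the correlation. A baseline-adjusted 30-day comparison exceeds both repeated measures terms at each correlation examined and tests 5C as written. All these figures rest on assumed alpha, effect size, equal SDs and correlations, with complete data on 30 per arm; they show the relative standing of the tests and do not forecast this trial's power.

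This is minor: one mechanism sub-hypothesis, on a questionnaire made for the study, in a pilot.

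**What to change.** For 5C, replace the number-of-assessments rule with a between-arm comparison of the 30-day Immediacy of Benefit score. If the item is also asked before randomisation, use that score only as a covariate (ANCOVA) and do not average it into the outcome. State at which visits each of the seven items is asked.

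Reword the Hypothesis 5 heading to predict more favourable mechanism variables at 30 days: shorter time to starting the regimen (5A), smaller increases for 5B, 5D, 5E and 5F, and a higher 30-day score for 5C.

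The cost is a few sentences in the SAP. No new data or visits are needed.
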